#### 7.2.4 Serious Adverse Event

An AE or SAR is considered “serious” if, in the view of either the investigator or DAIT, NIAID it results in any of the following outcomes (21 CFR 312.32(a) and ICH E2A):

1. Death
2. A life-threatening event: An AE or SAR is considered “life-threatening” if, in the view of either the investigator or DAIT, NIAID, its occurrence places the subject at immediate risk of death. It does not include an AE or SAR that, had it occurred in a more severe form, might have caused death.
3. Inpatient hospitalization or prolongation of existing hospitalization
4. Persistent or significant incapacity or substantial disruption of the ability to conduct normal life functions
5. Congenital anomaly or birth defect
6. Important medical event that may not result in death, be life threatening, or require hospitalization may be considered serious when, based upon appropriate medical judgment, it may jeopardize the subject and may require medical or surgical intervention to prevent one of the outcomes listed above.

Elective hospitalizations or hospital admissions for the purpose of conduct of protocol-mandated procedures (i.e. the 24-hour observation hospitalization for the drug infusion) are not to be reported as an SAE unless hospitalization is prolonged due to complications.

If an event meets any of the above SAE definitions, regardless of the relationship of the event to investigational product, the event must be reported to the sponsor as described in Section 7.5.2, *Reporting of Serious Adverse Events and Grade 3 and Higher Clinical Events*.

### 7.3 Collection and Recording of Adverse Events

#### 7.3.1 Investigational Product

The investigational product in this protocol is *ex vivo* Expanded Autologous CD4+CD127lo/-CD25+ Polyclonal Regulatory T Cells (PolyTregs).

#### 7.3.2 Methods of Collection

AEs (including SAEs) may be discovered through any of these methods:

- Observing the subject
- Questioning the subject in an objective manner
- Receiving an unsolicited complaint from the subject
- In addition, an abnormal value or result from a clinical or laboratory evaluation (including, but not limited to, a radiograph, an ultrasound, or an electrocardiogram) can also indicate an AE, as defined in Section 7.4, *Grading and Attribution of Adverse Events*. The evaluation that produced the result should be followed until that value or result returns to normal or can be explained and the subject’s safety is no longer at risk.

### 7.3.3 Methods of Recording

#### 7.3.3.1 Recording Adverse Events

Throughout the study, the investigator will record all clinical AEs and all laboratory AEs per the following criteria on the appropriate AE electronic case report form (eCRF) regardless of their severity or relation to study medication or study procedure.

- From time of signing of informed consent until start of investigational product infusion: all SAEs
- From start of investigational product infusion until 24 hours post infusion: all NCI-CTCAE Grade 1 and higher AEs
- From 24 hours post-infusion until Week 52: all NCI-CTCAE Grade 2 and higher AEs
- From Week 52 until Week 156: all SAEs and all NCI-CTCAE Grade 3 and higher AEs

Irrespective of study period, all clinical and laboratory events regardless of severity should be recorded in the medical research record for the duration of the trial.

The investigator will treat subjects experiencing AEs appropriately and observe them at suitable intervals until their symptoms resolve or their status stabilizes. Once recorded, an AE will be followed until it resolves with or without sequelae, or until the end of study participation, or after the subject prematurely withdraws (without withdrawing consent)/or is withdrawn from the study, whichever occurs first.

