For Grade 3 or higher AEs or any SAEs occurring in the second or third years of the study for each participant, DSMB input will be required for the evaluation of the following events unless the event was judged clearly unrelated to the investigational treatment:

- any Grade 4 or 5 AE
- two or more Grade 3 AEs of the same preferred term in a cohort

In addition to the pre-scheduled data reviews and planned safety monitoring, the DSMB will review any event that potentially impacts safety at the request of the SRC or DAIT, NIAID. The DSMB will have the discretion to recommend actions regarding study conduct and continuation as a consequence of any planned or unplanned monitoring activity.

Otherwise, the DSMB will be informed in real time per the following criteria:

- During Year 1 of each subject's participation:
  - any decision of the SRC to add additional subjects based on confirmation of a significant event (as defined as any related Grade 3 or higher AEs or any SAEs)
  - any malignancy
- During Years 2 and 3 of each subject's participation:
  - any Grade 3 event that is part of a pemphigus relapse/flare using the consensus definition of 3 or more new lesions a month that do not heal spontaneously within 1 week or by the extension of established lesions in a patient who has achieved disease control [58]
  - any malignancy

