### 5.6.4 Malignancies

As the T lymphocytes are one major component of tumor surveillance it is theoretically possible that cells that inhibit T lymphocytes could impair this function. Therefore, the recommendations for individuals at higher risk for skin cancer apply to this research population and exposure to sunlight and UV light should be limited by wearing protective clothing and using a sunscreen with high protection factor. Refer to Section 5.7, *Concurrent Medication and Therapy*.

Subjects over the age of 50 should have age-appropriate cancer screenings at the investigator's discretion prior to enrollment and throughout the course of the study. For additional information, consult the American Cancer Society (ACS) reference below:

<http://www.cancer.org/healthy/toolsandcalculators/reminders/screening-recommendations-by-age>

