## **7.5 Reporting of Adverse Events and Serious Adverse Events to the Sponsor: DAIT/NIAID**

### **7.5.1 Reporting of Adverse Events**

This section describes the responsibilities of the site investigator to report AEs to the study sponsor (DAIT/NIAID) via the DAIT-SACCC using the AE eCRF. Timely reporting of adverse events as specified by study phase in Section 7.3.3.1, *Recording Adverse Events* is expected.

Unless otherwise noted below in Section 7.5.2, *Reporting of Serious Adverse Events and Grade 3 and Higher Clinical Events*, for serious adverse events and events of special interest, AEs should be recorded on the AE eCRF within five (5) business days of the site learning of the event(s). Whenever possible, a diagnosis should be provided, rather than compilation of signs/symptoms, with grade of the event determined by highest grade of the sign/symptom component.

The exception to this reporting timeframe is the reporting of serious adverse events and Grade 3 or higher clinical events which require reporting within 24 hours of discovery as described in Section 7.5.2 below.

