### **7.5.2 Reporting of Serious Adverse Events and Grade 3 and Higher Clinical Events**

This section describes the responsibilities of the site investigator to report serious adverse events and non-serious Grade  $\geq 3$  events to the sponsor via the electronic CRF (eCRF). Timely reporting of adverse events is required by 21 CFR and ICH E6 guidelines.

The adverse events outlined below must be reported by the site investigators to DAIT/NIAID via the DAIT-SACCC regardless of relationship or expectedness to study intervention **within 24 hours of discovery of the event:**

- All SAEs per 21 CFR 312.32 definitions (see Section 7.2.4, *Serious Adverse Event*)
- All other Clinical events with a NCI-CTCAE Grade 3 or greater severity

*Note: clinical events include signs/symptoms, diagnoses, and laboratory abnormalities with clinical consequence (defined as the requirement for intervention, correction, increased monitoring, or further evaluation). Inclusive in this category is any NCI-CTCAE Grade 3 or greater clinical/laboratory component associated with a pemphigus relapse/flare per protocol Section 3.4.1 Exploratory Safety Endpoints.*

The SAE eCRF will be used to capture all SAEs and non-serious Grade  $\geq 3$  clinical events for submission to the sponsor (DAIT/NIAID). All requested information on the SAE eCRF should be provided. Unavailable details of the event at the time of the initial report should not delay submission of known information. The initial report should include at a minimum: AE term, relationship to PolyTregs, and as applicable, reason why event is serious per the definitions in Section 7.2.4 *Serious Adverse Event*.

Supplementary CRF pages including medical history, concomitant medications, demographics, study drug administration, and death must be provided as applicable. As additional details become available, the SAE eCRF should be updated and submitted. With

each iteration of the form, the investigator (or designated sub-investigator) must sign the form electronically.

For additional information regarding SAE reporting, contact Rho Product Safety (DAIT-SACCC):

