##### 7.8.3 DSMB Review

The DSMB will review the safety data collected when the fourth subject in cohort 1 completes Week 8. In addition, the DSMB will review accumulating safety data at least yearly during planned DSMB Data Review Meetings. Data for the planned safety reviews will include, at a minimum, a listing of all reported AEs and SAEs. To ensure subject safety between Data Review Meetings, the DSMB will be informed of all expedited safety reports in a timely manner.

In addition to the pre-scheduled data reviews and planned safety monitoring, the DSMB may be called upon for ad hoc reviews or emergency meetings (see Section 5.5.4, *Safety Stopping Guidance*). The DSMB will have the discretion to recommend actions regarding study conduct and continuation as a consequence of any planned or unplanned monitoring activity.

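### The DSMB is to hear of any malignancy in real time through Year 3, but site reporting rules give no route for a non-serious case below Grade 3

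*Combined protocol and SAP*

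**What the plan says.** **The duty to the DSMB.** After listing the events that need DSMB input, Section 5.5.4 adds a second tier: "Otherwise, the DSMB will be informed in real time per the following criteria". Malignancy of any kind is on that list for Year 1 and again for Years 2 and 3.

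**What sites enter on the eCRF.** Section 7.3.3.1 sets a threshold by period: SAEs only before infusion, Grade 1 and above for the first 24 hours, Grade 2 and above to Week 52, and then "From Week 52 until Week 156: all SAEs and all NCI-CTCAE Grade 3 and higher AEs". Everything else stays in the site's medical research record.

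**What sites report within 24 hours.** Section 7.5.2 lists all SAEs and "All other Clinical events with a NCI-CTCAE Grade 3 or greater severity". A note adds pemphigus flares: "Inclusive in this category is any NCI-CTCAE Grade 3 or greater clinical/laboratory component associated with a pemphigus relapse/flare". Malignancy is not mentioned.

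**Routine timing.** Section 7.5.1, subject to exceptions in Section 7.5.2, reads: "for serious adverse events and events of special interest, AEs should be recorded on the AE eCRF within five (5) business days". The special-interest events are placed among those exceptions, but Section 7.5.2 names none.

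**What the DSMB sees at planned reviews.** Section 7.8.3: "Data for the planned safety reviews will include, at a minimum, a listing of all reported AEs and SAEs".

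**The concern.** A notice duty works only if the site must tell the sponsor. For malignancy, the duty in Section 5.5.4 is wider than the rules that feed it, and the shortfall is largest in Years 2 and 3, when the recording threshold is highest.

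Loss of tumor surveillance is a named risk of the product (Sections 1.5.2.5 and 5.6.4). Section 5.6.4 treats these subjects as being at raised risk of skin cancer and says: "Subjects over the age of 50 should have age-appropriate cancer screenings". That screening is left to the investigator, but it extends through the study. Exclusion 26 admits people with fully treated basal cell carcinoma. Table 6.1 schedules a physical examination at Weeks 78, 104, 130 and 156. A small skin cancer found and removed at one of those visits is a plausible case.

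If it were graded below 3 and not judged serious, it could be missing from the real-time notice, the DSMB listing, the AE tables in Section 8.3.1 and the secondary endpoint of all AEs through Week 156. With at most 12 infused subjects, one missed malignancy would matter to the safety profile.

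**Working it through.** The plan gives no figure on this point, and Table 8.1 (the chance of seeing at least one significant event) does not bear on it. The check compares the rules.

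**Step 1. Which DSMB triggers do the recording rules support?** Bullets in Section 5.5.4:

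- DSMB input required: 4 in Year 1, 2 in Years 2 and 3.
- DSMB informed: 2 in Year 1, 2 in Years 2 and 3.
- Total: 4 + 2 + 2 + 2 = 10.
- Resting on Grade 3 or higher AEs or on SAEs: 4 + 2 + 1 + 1 = 8. Section 7.3.3.1 records these from infusion through Week 156.
- Malignancy without limit: 1 + 1 = 2. These are only partly supported.

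**Step 2. What happens to a malignancy not judged serious?** From Sections 7.3.3.1, 7.5.1 and 7.5.2:

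| Period | Grade 1 | Grade 2 | Grade 3 or higher |
|---|---|---|---|
| Consent to infusion | no entry | no entry | 24-hour report |
| Infusion to 24 hours | AE eCRF, 5 business days | AE eCRF, 5 business days | 24-hour report |
| 24 hours to Week 52 | no entry | AE eCRF, 5 business days | 24-hour report |
| Week 52 to Week 156 | no entry | no entry | 24-hour report |

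The lead-in to Section 7.3.3.1 speaks of recording whatever the severity, but makes this subject to the period criteria, which are grade thresholds. It does not fill the empty cells.

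**Step 3. How long is the gap?** For Grade 2: 156 − 52 = 104 weeks, and 104 / 156 = 67% of post-infusion follow-up. Before Week 52 the problem for Grade 2 is delay and the absence of any flag, not loss. For Grade 1 the gap runs from 24 hours after infusion to Week 156. In no period does a non-serious malignancy below Grade 3 trigger 24-hour reporting.

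**Step 4. Do other routes close it?**

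- *Important medical event (Section 7.2.4).* An event may be classed as serious if "it may jeopardize the subject and may require medical or surgical intervention to prevent one of the outcomes listed above". This is optional and rests on medical judgment; cancer is not serious by default. The sponsor may also make the call, but only for a case it knows about.
- *Unanticipated problems (Section 7.7).* Notice is prompt, but the site must first decide that the event qualifies.
- *Monthly study management reports (Section 7.8.1) and SRC listings (Section 8.4.1).* The monthly reports compile what sites put on eCRFs, and the AE listings depend on recorded AEs, so neither supplies an unrecorded case.
- *Source audits (Section 10).* These are periodic, so not real time.

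**Step 5. Compare the flare trigger.** Section 5.5.4 names Grade 3 flare events, and Section 7.5.2 expressly places Grade 3 or greater flare components on the 24-hour list. For flares the duty and the route match. For malignancy there is a duty and no counterpart.

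**The case against.** The strongest reply is that the gap may be empty. It needs a malignancy that is both below Grade 3 and not judged serious, and the documents do not show how the CTCAE grades malignancies. With tumor surveillance a named risk, an investigator or the sponsor may well class any new cancer as an important medical event, which brings the 24-hour report and eCRF entry through Week 156. Seriousness is always a judgment, so every SAE-based trigger shares that dependence. This stands as a limit on how often the gap would matter. It does not remove the mismatch: Section 5.5.4 makes notice of malignancy independent of seriousness, while the site rules make it depend on grade or seriousness.

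A second reply is that the real-time list follows text about Grade 3 or higher AEs and SAEs, so its malignancy bullets might carry the same limit. That reading is hard to sustain. The neighboring flare bullet for Years 2 and 3 states its own Grade 3 limit, which would be redundant if the whole list were already restricted.

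Third, counting bullets does not measure risk, and both malignancy bullets are partly covered: serious and Grade 3 or higher cases within 24 hours, Grade 2 cases in Year 1 within 5 business days. That is fair; the count shows only where the rules and the duty part.

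Finally, the Manual of Procedures is not available here and may hold an instruction, and about four sites could escalate informally. Both are possible, but the protocol does not require either for malignancy.

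**Conclusion.** The concern holds. As written, the protocol commits to real-time DSMB notice of every malignancy for three years without giving sites a rule that delivers it for non-serious cases below Grade 3. The gap is 104 of 156 weeks for Grade 2 and nearly all post-infusion follow-up for Grade 1.

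The number of cases affected is unknown. The assumption is that some malignancies are both below Grade 3 and judged non-serious. At one end of the range, all are Grade 3 or higher or classed as important medical events, and none is missed. At the other, every such case after Week 52 is left to audit or voluntary notice.

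The primary endpoint, dose-escalation rules and sample size are untouched. This is a correction that should be made to the monitoring of a named risk, not a flaw in the design.

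**What to change.** - **Section 7.3.3.1:** require eCRF entry of any malignancy, regardless of grade or seriousness, from infusion through Week 156.
- **Section 7.5.2:** add any malignancy to the 24-hour list and identify it as the event of special interest to which Section 7.5.1 refers. The notice in Section 5.5.4 then has a route.
- **Section 8.3.1 (optional):** a separate malignancy row. Recorded cases already appear by preferred term.

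The cost is one line and one bullet. Sites already note all events in the medical research record, so no visits, procedures or staff are added.

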#### 7.3.3.2 Recording Serious Adverse Events

Serious AEs will be recorded on the appropriate AE/SAE eCRF. All requested information on the AE eCRF and SAE eCRF should be provided, if available, for submission to the DAIT-SACCC, DAIT, NIAID, and health authorities as outlined in Section 7.5, *Reporting of Adverse Events and Serious Adverse Events to the Sponsor: DAIT/NIAID*.

Once recorded, an SAE will be followed until it resolves with or without sequelae, or until the end of study participation, whichever occurs first. End of study participation is the final study visit, either at time of study completion or when a subject prematurely withdraws or is withdrawn.

## 7.4 Grading and Attribution of Adverse Events

### 7.4.1 Grading Criteria

The study site will grade the severity of AEs experienced by the study subjects according to the criteria set forth in the NCI-CTCAE v4.0. This document (referred to herein as the NCI-CTCAE manual) provides a common language to describe levels of severity, to analyze and interpret data, and to articulate the clinical significance of all AEs. The NCI-CTCAE has been reviewed by the Protocol Chairs and has been deemed appropriate for the subject population to be studied in this protocol.

AEs will be graded on a scale from 1 to 5 according to the following standards in the NCI-CTCAE manual:

Grade 1 = mild AE

Grade 2 = moderate AE

Grade 3 = severe and undesirable AE

Grade 4 = life-threatening or disabling AE

Grade 5 = death

If NCI-CTCAE criteria are defined for grading an abnormal value or result from a clinical or laboratory evaluation (including, but not limited to, a radiograph, an ultrasound, or an electrocardiogram), then a treatment-emergent AE is defined as an increase in grade from Baseline (Day 0) or from the last post-baseline value that doesn't meet grading criteria. Changes in grade from screening to Baseline (Day 0) will also be recorded as outlined in Section 7.3.3.1, *Recording Adverse Events*. If a specific event or result from a given clinical or laboratory evaluation is not included in the NCI-CTCAE manual, then an abnormal result would be considered an AE if changes in therapy or monitoring are implemented.

AEs that are related to disease activity will be graded according to the plan outlined above. However, an increase in disease activity leading to an AE should also be reflected in standard measures of disease activity (PDAI) measured at regularly scheduled visits.

To facilitate identification of a safety signal associated with increased disease activity, the PDAI disease activity measures will be used throughout the study to monitor changes in disease activity over time. The DSMB will receive reports on these assessments for each cohort at regularly scheduled reviews.

#### 7.4.2 Attribution Definitions

The relation, or attribution, of an AE to an investigational product will initially be determined by the site investigator. The site investigator will also record the initial determination of attribution on the appropriate AE eCRF. Final determination of attribution for safety reporting will be decided by DAIT, NIAID with input from the SRC. The relationship of an adverse event to study therapy regimen or procedures will be determined using the descriptors and definitions provided in Table 7.1 (below).

**Table 7.1 Attribution of Adverse Events**

Code	Descriptor	Relationship (to primary investigational product and/or other concurrent mandated study therapy or study procedure)
Unrelated Categories		
1	Not Related	The adverse event is clearly not related: there is insufficient evidence to suggest a causal relationship.
Related Categories		
2	Possibly Related	The adverse event has a reasonable possibility to be related; there is evidence to suggest a causal relationship.
3	Related	The adverse event is clearly related.

## **7.5 Reporting of Adverse Events and Serious Adverse Events to the Sponsor: DAIT/NIAID**

### **7.5.1 Reporting of Adverse Events**

This section describes the responsibilities of the site investigator to report AEs to the study sponsor (DAIT/NIAID) via the DAIT-SACCC using the AE eCRF. Timely reporting of adverse events as specified by study phase in Section 7.3.3.1, *Recording Adverse Events* is expected.

Unless otherwise noted below in Section 7.5.2, *Reporting of Serious Adverse Events and Grade 3 and Higher Clinical Events*, for serious adverse events and events of special interest, AEs should be recorded on the AE eCRF within five (5) business days of the site learning of the event(s). Whenever possible, a diagnosis should be provided, rather than compilation of signs/symptoms, with grade of the event determined by highest grade of the sign/symptom component.

The exception to this reporting timeframe is the reporting of serious adverse events and Grade 3 or higher clinical events which require reporting within 24 hours of discovery as described in Section 7.5.2 below.

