Since a significant event in this trial can occur from toxicity from the study drug or disease worsening (e.g., a pemphigus flare), the standard 3 + 3 design rules for dose escalation will not be employed. Therefore, if a Grade 3 or higher AE or any SAE occurs in a subject during his/her first year of study participation, enrollment will be suspended until the SRC can convene to review the event. If this occurs, the SRC may decide at that time to proceed with enrollment, adjust the dose as described above, continue the suspended enrollment until the Data and Safety Monitoring Board (DSMB) can review the data, or place the trial on hold. The SRC will review all Grade 3 or higher AEs or any SAEs that occur throughout the study. However, since the likelihood of events being related to the investigational treatment diminishes over time, Grade 3 or higher AEs or any SAEs occurring during a subject's second or third year of the study will not result in an immediate suspension of enrollment, donation, and treatment, unless the SRC determines that such action is indicated. Provided the SRC can review the event within 5 business days of awareness, events judged to be significant will drive protocol management in terms of proceeding, suspending enrollment/treatment pending ad hoc DSMB input, or placing the study on hold pending further evaluation.

DSMB input will be required for the evaluation of some specific events. Description of these events and additional directives are outlined in Section 5.5.4, *Safety Stopping Guidance*.

Accrual of all subjects is expected to take approximately 1.5 years.

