#### 5.5.4 Safety Stopping Guidance

The SRC will suspend enrollment after a Grade 3 or higher AE or any SAE (as described in Section 3.1, *Description of Study Design*) in this trial in order to review the event, to review any additional events that occurred in the trial, and to make a decision on how to proceed. In the event of a temporary suspension in enrollment for a Grade 3 or higher AE or any SAE or a post release positive sterility result (see Section 5.3.3, *Action Plan for Post Release Positive Sterility Results*), no new subjects will be consented or started on therapy with PolyTregs; subjects who already received PolyTregs will continue to be followed. Subjects in the screening phase of the study may continue screening procedures (e.g., blood tests), but a skin biopsy to confirm Inclusion Criteria # 3 (see Section 4.1, *Inclusion Criteria*) should be deferred. Enrollment will not occur until the SRC review is complete.

A significant event in this trial can occur either due to toxicity from the study drug or disease worsening (e.g., a pemphigus relapse/flare) assessed as related to the investigational treatment.

The SRC will make this determination, seeking advice from the DSMB, if necessary. After SRC review, the study will: 1) proceed with enrollment as originally planned, 2) continue to suspend enrollment until the DSMB can review and advise on the event, or 3) be placed on hold pending further evaluation of the event, consideration of potential study modifications, and review by the DSMB, IRB and FDA.

For Grade 3 or higher AEs or any SAEs occurring in the first year of the study for each participant, DSMB input will be required for the evaluation of the following events unless the event was judged clearly unrelated to the investigational treatment:

- two Grade 3 or higher AEs or SAEs that occurs during the first 12 weeks of each participant in each cohort
- any Grade 4 or 5 AE
- two or more Grade 3 AEs of the same preferred term in a cohort
- any Grade 3 AE that is part of a pemphigus relapse/flare using the consensus definition of 3 or more new lesions a month that do not heal spontaneously within 1 week or by the extension of established lesions in a patient who has achieved disease control [58]

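### A non-serious Grade 3 or higher laboratory AE that the site judges to need no action triggers the first-year hold, yet may be reported up to 5 business days later

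*Combined protocol and SAP*

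**What the plan says.** **The trigger.** Under Section 3.1, if "a Grade 3 or higher AE or any SAE occurs in a subject during his/her first year of study participation, enrollment will be suspended". Section 5.5.4 repeats it: "The SRC will suspend enrollment after a Grade 3 or higher AE or any SAE". Neither section filters by relatedness, or by whether the AE is clinical or laboratory.

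**What the hold stops.** Section 5.5.4 says that "no new subjects will be consented or started on therapy with PolyTregs". It does not name blood donation. Section 3.1 names donation only when it exempts second- and third-year events, which "will not result in an immediate suspension of enrollment, donation, and treatment".

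**When a laboratory value is an AE.** Where CTCAE grades exist for a result, Section 7.4.1 says "a treatment-emergent AE is defined as an increase in grade from Baseline (Day 0", or from the last later value that met no grade. No clinical consequence is needed. Section 7.3.3.1 has Grade 2 and higher AEs recorded from 24 hours after infusion to Week 52, so these events are captured. Only the timing is in question.

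**The deadlines.** The default in Section 7.5.1 is that "AEs should be recorded on the AE eCRF within five (5) business days of the site learning of the event(s". The 24-hour list in Section 7.5.2 has two entries: SAEs, and "All other Clinical events with a NCI-CTCAE Grade 3 or greater severity". A note there counts a laboratory abnormality as clinical only if it calls for treatment, correction, closer monitoring or more work-up, or is a Grade 3 or higher component of a pemphigus flare. The opening sentence of 7.5.2 describes the duty as covering non-serious Grade 3 or higher events and does not limit it to clinical ones.

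**The concern.** The events that stop the trial form a wider set than the events that must be reported in time to stop it. The Safety Review Committee (SRC) imposes the hold, so it cannot act on an event it has not been told about. About four sites are expected, and what one site knows does not by itself stop another from collecting blood or infusing.

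The plan relies on spacing between subjects to limit risk at each dose. If a qualifying event sits unreported for a week, a step that the hold is meant to stop can go ahead. A Grade 4 laboratory AE in this position would also need Data and Safety Monitoring Board (DSMB) input under Section 5.5.4 unless judged clearly unrelated.

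No other route brings the news sooner. The study management team's reports are monthly (7.8.1). The medical monitor is sent SAE and pregnancy reports (7.8.2). The SRC's 5-business-day review in Section 3.1 runs from awareness.

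**Working it through.** The plan states no figure for this lag, so the check compares the two event sets and then works through the calendar.

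**Step 1. Which first-year events fall in the gap**

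| First-year AE | Triggers hold (3.1, 5.5.4) | Deadline (7.5.1, 7.5.2) |
|---|---|---|
| Any SAE | Yes | 24 hours |
| Grade 3+ sign, symptom or diagnosis | Yes | 24 hours |
| Grade 3+ laboratory AE leading to any action, monitoring or work-up, or part of a flare | Yes | 24 hours |
| Non-serious Grade 3+ laboratory AE with none of these | Yes | 5 business days |

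Only the last row is mismatched.

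**Step 2. Inputs for the calendar**
- The next donation waits until the prior subject reaches Week 2 (Section 3.1). The Week 2 window is 14 ± 3, or Day 11-17 (Table 6.1).
- The Week -2 visit is on Day -16 to -14 (Table 6.1), so infusion follows donation by 14 to 16 days.
- Scheduled hematology after infusion is at Weeks 1, 2, 8 and 12, then at each later visit. The first scheduled chemistry is at Week 8, 56 ± 7, or Day 49-63 (Table 6.1).
- Five business days is 7 calendar days for a weekday discovery, 6 for a Saturday and 5 for a Sunday, and longer with a holiday. I use 7.
- Assumptions: the result is known on the day of the draw, the site uses the full allowance, and subjects follow one another as fast as allowed.

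**Step 3. The next subject's donation**
- Latest entry of a Week 2 result: 11 + 7 = Day 18 to 17 + 7 = Day 24.
- Earliest next donation: Day 11-17, so it can precede entry.
- A nominal Week 1 result (Day 7) may be entered as late as 7 + 7 = Day 14, the nominal donation day.

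**Step 4. The next subject's infusion**
- Second infusion: 11 + 14 = Day 25 to 17 + 16 = Day 33.
- If donation is on the day of the Week 2 visit, entry is due by visit + 7 and infusion is at visit + 14 or later, a margin of 7 days.
- Even setting the latest entry (Day 24) against the earliest infusion (Day 25), entry comes first.

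**Step 5. A later subject's infusion**
- Third infusion: 2 × 25 = Day 50 to 2 × 33 = Day 66.
- Latest entry of the first subject's Week 8 results: 49 + 7 = Day 56 to 63 + 7 = Day 70.
- On nominal visit days, the third infusion is at 2 × (14 + 14) = Day 56 to 2 × (14 + 16) = Day 60. A Day 56 result may be entered until Day 63. The infusion can come first.

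**Step 6. Effect of a 24-hour rule**
- Longest time from discovery to notice: 7 days falls to 1.
- Longest time to the end of the SRC's review, counting 5 business days from notice: 7 + 7 = 14 days falls to 1 + 7 = 8.

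**The case against.** The strongest reply is that the gap is close to empty. The 7.5.2 note is broad, and Section 7.3.2 asks that the evaluation behind an abnormal result be followed until it is normal, or explained with the subject no longer at risk. A new Grade 3 or 4 value would normally lead to a repeat test, which can be read as increased monitoring or further evaluation and so moves to the 24-hour route. This largely stands, and it makes the gap narrow. It does not close it: the classification is left to the site, while the hold is not discretionary, and the opening of 7.5.2 and its own list disagree.

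Section 7.4.1 describes Grade 4 as life-threatening or disabling, so some Grade 4 values would be handled as SAEs. That also stands, but it is not automatic. In the earlier type 1 diabetes trial (1.3.2.1.3), two Grade 4 hypoglycemia events and a Grade 3 elevated D-dimer are not among the five SAEs listed.

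A reader might infer more than the documents support:
- *That the next subject can be infused before the sponsor hears of a scheduled result.* Step 4 shows otherwise under its assumptions. That would take an unscheduled or late-learned result.
- *That donation is plainly barred during a hold.* This is implied by the later-year exemption in 3.1. It is not stated in 5.5.4, and donation alone delivers no study product.
- *That the lag as a share of the interval between infusions measures risk.* It does not. The lag matters only after a qualifying result, and scheduled results come at a few fixed visits.
- *That the eCRF report is the only link between sites.* The stagger itself needs cross-site confirmation, all product comes from one facility, and central-laboratory data are transferred electronically (Section 10). None of these is tied to the hold, but the documents do not show that nothing else could carry the news.

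Finally, the carve-out in 7.5.2 may be deliberate and the trigger loosely worded. The documents do not settle which, so the firm conclusion is that the sections need reconciling.

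**Conclusion.** The mismatch is real and narrow. One class of event, the non-serious Grade 3 or higher laboratory AE that the site thinks needs no action or follow-up, triggers a mandatory first-year hold but carries a reporting allowance of about 7 calendar days.

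From scheduled tests, the immediate exposure is the next subject's 400 ml donation, if the hold is taken to cover donation. Infusion ahead of the report is possible for a third subject. It requires the fastest stagger, a qualifying Week 8 result in the first subject, a site judgement that nothing further is needed, and use of most or all of the allowance. Five business days is a maximum, and a site may report sooner.

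How often such an event would arise cannot be estimated from the documents. The analysis is not at stake, since the events are still recorded. The point concerns when the hold can take effect, and it is worth correcting because the correction is easy.

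**What to change.** Reconcile Sections 3.1, 5.5.4, 7.5.1 and 7.5.2 so that the events that trigger the first-year hold and the events reported within 24 hours are the same set. The simplest way is to have 7.5.2 require a 24-hour report of every Grade 3 or higher AE, laboratory or clinical, during each subject's first year, with the exception in 7.5.1 worded to match. This also removes the conflict between the opening of 7.5.2 and its list. If the laboratory carve-out is intended, the sponsor should say so and explain how it fits the trigger. Section 5.5.4 should also state whether donation is within the hold.

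The cost is a sentence or two and a few more 24-hour forms in at most twelve infused subjects. The reporting change adds no holds beyond those that 3.1 already requires, though some will be called for values later judged unimportant.
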